1.1 General Introduction

Acute myeloid leukemia (AML) is a genetically and phenotypically very heterogeneous disorder with an incidence of 3 to 4 per 100 000 men and women per year with a median age at diagnosis ranging from 66 to 71 years [1][2]. It is characterized by the accumulation of somatically acquired genetic changes in hematopoietic progenitor cells that alter normal mechanisms of self-renewal, proliferation, and differentiation. Outcome is influenced by various factors, including patient features such as age, comorbidities, and performance status and disease characteristics of which the genetic profile of the disease is the most important. According to the recommendations from an international expert panel, on behalf of the European LeukemiaNet (ELN), AML can be grouped into 3 risk groups, favorable, intermediate and unfavorable [1]. In patients considered suitable for intensive induction therapy, the combination of an anthracycline and cytarabine remains the standard of care. Complete remission (CR) can be achieved in 65% to 75% of younger adult patients (≤ 60 years) and in approximately 40% to 60% of older patients (> 60 years). In patients who achieve a CR after induction chemotherapy, some postremission therapy (PRT) is required to prevent relapse [1][2][3]. Although the value of PRT in the older patients continues to be debated, in younger patients, the choice for consolidation is based on genetic features and can range from high dose cytarabine to allogeneic hematopoietic cell transplantation (alloHCT), with a 5-year overall survival (OS) rate of 40% to 45%; OS in older patients still remains poor at $< 10\%$ after 5 years [1][3]. In patients ineligible for intensive chemotherapy, the spectrum of treatment options is limited and includes best supportive care with hydroxyurea, low-dose cytarabine, and the hypomethylating agents decitabine or azacitidine. Using such low-dose therapy, CR can be achieved in 10% to 30% of patients and the OS at 3 years is approximately 5% [1][2].

Beyond pre-treatment risk stratification, measurement of the disease burden named measurable residual disease (MRD) during treatment and follow up emerges as one of the most important prognostic factors once a CR of the disease is achieved [4][5][6][7][8][9].

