MRD assessed by flow-cytometry as described previously [5][6][7][8][21][22][23][24][25][26][27] is assessed in patients after induction (newly diagnosed AML) or salvage chemotherapy (relapsed/refractory AML) and after completion of consolidation therapy (newly diagnosed AML and relapse/refractory AML) in the two laboratories at the University Hospital Heidelberg and the University Hospital Dresden. MRD assessed by MPFC will be evaluated first at the same time as the remission status based on morphology after induction/salvage therapy. This MRD assessment by MPFC after induction/salvage therapy is used to test the primary hypothesis. A second MRD assessment by MPFC will be performed after completion of consolidation therapy including high-dose chemotherapy and alloHCT. MRD positive values are documented as discrete numbers up to 100%.

[figure not shown]
9.1.2 Standard assessment:

Overall survival (OS) is defined as time from entry into the study until death from any cause. Event-free survival (EFS) is measured from entry into the study until one of the following events, whichever comes first, i) no response to induction therapy, ii) relapse, iii) death from any cause. For assessment of response to induction therapy and relapse, morphological evaluation of peripheral blood and bone marrow smears is the standard assessment. Relapse-free survival (RFS) is measured in patients who achieve a first CR. RFS is measured from achievement of first CR until one of the following events, whichever comes first i) relapse, ii) death from any cause. For assessment of relapse morphological evaluation of peripheral blood and bone marrow smears is the standard assessment. OS, EFS, and RFS are censored at the date of last follow up in case of no event. The survival endpoints OS, EFS, and RFS defined according to the ELN recommendations [1] are accepted standards. Within the proposed study the primary survival endpoint is OS, EFS and RFS are included as secondary survival endpoints.

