The figure illustrates the correlation of the treatment effects on EFS and OS from 7 independent treatment comparisons as outlined and numbered in the table on the left. In this example clearly a substantial treatment effect could be demonstrated in 4 of the 7 treatment comparisons. Based on this experience we also expect treatment effects in most of the trials being part of the application. The sample size of the proposed study is fixed by the limited number of randomized trials and the trial-individual sample size calculation. We assume that 1000 patients are eligible for MRD assessment by MPFC after induction/salvage therapy. Based on i) our previous experience showing a high correlation of treatment effects on EFS and OS ($R=0.99$ for log hazard ratios with lower 95% confidence limit of 0.85), ii) the compelling data available on the prognostic value of MRD assessed by MPFC [5][21][22][23][24][25][26][27] and iii) the growing body of evidence indicating efficacy of new drugs especially in combination with induction/salvage therapy and not or to a much lesser extend later on in the treatment course (consolidation, maintenance) [10][32][49][50] the primary hypothesis is that MRD assessment by MPFC after induction/salvage therapy is a good surrogate for OS defined by trial level correlation R_T of the treatment effects on MRD assessed by MPFC and OS with $R_T > 0.8$.

We aim to test the one-sided null hypothesis $H_0: R_T \leq 0.8$ against the alternative hypothesis $H_1: R_T > 0.8$ at a significance level of $\alpha = 2.5\%$. To this aim we will use an individual patient data (IPD) meta-analytic approach and focus on the coefficient of determination (R_T)² to quantify the strength of association between treatment effects on MRD assessed by MPFC (log odds ratios, derived by logistic regression models) and treatment effects on OS (log hazard ratios, using Cox regression models) at the trial level. Based on the given sample size of at least 1000 patients within the included randomized clinical trials and considering a true R_T of 0.9 the power to identify this effect will be larger than 85%.

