9.1.4 Statistical Analysis

With respect to Prentice's original proposal [36] current consensus is that for surrogate validation a correlation-based approach can be applied, with estimation of correlation measures on a trial level and an individual patient level [51][52][53]. We will apply the correlation approach according to Buyse et al. [40] to investigate the validity of MRD assessed by MPFC as surrogate endpoint for the long-term time to event endpoints OS (primary endpoint), RFS, and EFS (secondary endpoints). Two levels of surrogacy will be considered. On an individual patient level we will assess how well the surrogate predicts the survival endpoint. This is done by evaluating the prognostic value of MRD assessed by MPFC for the survival endpoint after adjustment for treatment. We will use the R^2 measure of Schemper and Henderson as well as Brier Score to assess the predictive accuracy of MRD assessed by MPFC [54]. Within the trial-level evaluation an individual patient data (IPD) meta-analytical approach will be used to test if the treatment effect on MRD assessed by MPFC allows reliable prediction of the treatment effect on the survival endpoints. We consider logistic regression for the surrogate endpoint MRD assessed by MPFC to achieve odds ratios (OR) and the proportional hazards model of Cox for the survival endpoints resulting in per trial hazard ratios (HR) and an error-in-variables linear

regression model of the log transformed HRs on the log transformed ORs. The trial-level coefficient of determination R_T^2 is then used to quantify the strength of association between the treatment effects on MRD assessed by MPFC and on the survival endpoints at the trial level.

In addition the surrogate threshold effect (STE) [42] will be estimated as the minimum effect of MRD assessed by MPFC that predicts a statistically significant effect on EFS, RFS and OS.

In addition, exploratory analyses will be performed on

- MRD assessed by MPFC after consolidation as a surrogate for OS, EFS and RFS
- Correlation of MRD assessed by MPFC after induction therapy and after consolidation therapy with respect to applied postremission treatment

A detailed statistical analysis plan (SAP) will be finalized before database closure.

10 Quality assurance and monitoring

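### RFS is defined only in patients who reach CR, so its per-trial hazard ratio is not a randomised effect and should not enter the trial-level surrogacy model or a surrogate threshold effect

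*Combined protocol and SAP*

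**What the plan says.** Section 9.1.2 gives the survival endpoints different populations and time origins. For overall survival: "Overall survival (OS) is defined as time from entry into the study until death from any cause". EFS also starts at study entry, and non-response to induction counts as an event. For RFS, "Relapse-free survival (RFS) is measured in patients who achieve a first CR", and "RFS is measured from achievement of first CR until one of the following events", namely relapse or death.

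Section 9.1.4 treats the three alike. It sets out to validate MRD as a "surrogate endpoint for the long-term time to event endpoints OS (primary endpoint), RFS, and EFS (secondary endpoints". At trial level it uses "the proportional hazards model of Cox for the survival endpoints resulting in per trial hazard ratios (HR"), regresses the log hazard ratios on the MRD log odds ratios with an error-in-variables model, and summarises the fit by R_T². It also defines an STE as the smallest MRD effect that "predicts a statistically significant effect on EFS, RFS and OS".

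Two further statements matter. Section 9.1.3 cites evidence for "efficacy of new drugs especially in combination with induction/salvage therapy and not or to a much lesser extend later on" in the treatment course. Section 1.1 gives the starting CR rates: "Complete remission (CR) can be achieved in 65% to 75% of younger adult patients" and roughly 40% to 60% in older ones.

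Nothing in the protocol corrects RFS for selection by CR, defines a version in all randomised patients, or confines RFS to individual-level use.

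**The concern.** Trial-level surrogacy relates one treatment effect to another across randomised trials. OS and EFS hazard ratios qualify because every randomised patient counts from entry. An RFS hazard ratio qualifies only if reaching CR is unrelated to treatment. A drug that works in induction or salvage may raise the CR rate. The better arm's RFS set then contains extra patients who reached CR only because of the drug. If their outlook is worse than that of patients who would have reached CR anyway, the RFS comparison is tilted against the better arm.

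Two outputs are at stake: the RFS value of R_T² and the RFS STE. Section 9.1 explains that an STE could be used to design future trials, so an STE resting on a selected comparison could mislead beyond this study.

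**Working it through.** The documents give no figure for RFS at trial level, so there is none to reproduce. The check has two parts: how far selection by CR can move the RFS hazard ratio, and what that does to R_T².

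**Inputs.** CR of 60% on control and 75% on experimental lies within the span of CR rates in Section 1.1. Everything else is an assumption. There are three groups: always-CR (60%), converted, meaning CR only on the experimental arm (15%), and never-CR (25%). The relapse hazard is 0.4 per year in always-CR patients and h_C = 0.7 or 1.0 in converted patients. The death hazard is 1.0 per year after relapse or without CR. Follow-up is 3 years. MRD negativity is 60% in always-CR, 40% in converted and nil in the rest. θ is the true hazard ratio in always-CR patients.

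**Step 1, make-up of the RFS sets.** Control: always-CR only. Experimental: 15/75 = 20% converted, 80% always-CR.

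**Step 2, RFS hazard ratio.** At the moment of CR it is (0.80 × 0.4 × θ + 0.20 × h_C) / 0.4. It then falls, because converted patients relapse sooner and leave the risk set. The last column is the Cox estimate over follow-up from simulation.

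| θ | h_C | Ratio at CR | Cox RFS HR |
|---|---|---|---|
| 1.00 | 0.7 | (0.32 + 0.14)/0.4 = 1.15 | 1.10 to 1.12 |
| 1.00 | 1.0 | (0.32 + 0.20)/0.4 = 1.30 | about 1.15 (up to 1.18 in separate runs) |
| 0.85 | 0.7 | (0.272 + 0.14)/0.4 = 1.03 | 0.97 to 0.99 |
| 0.70 | 0.7 | (0.224 + 0.14)/0.4 = 0.91 | 0.82 to 0.85 |
| 1.00 | 0.4 | (0.32 + 0.08)/0.4 = 1.00 | 1.00 |

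In the first two rows the simulated OS hazard ratio is about 0.87 to 0.90, a benefit. In the last row, where converted patients have the always-CR prognosis, RFS is neutral while OS still improves (about 0.82).

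**Step 3, the MRD odds ratio under two denominators.**
- All patients: negativity is 0.60 × 0.60 = 0.36 on control and 0.36 + 0.15 × 0.40 = 0.42 on experimental. Log OR = ln[(0.42/0.58)/(0.36/0.64)] = +0.25, a benefit, like OS.
- CR patients only: 0.60 on control and 0.42/0.75 = 0.56 on experimental. Log OR = ln[(0.56/0.44)/(0.60/0.40)] = −0.16, an apparent harm, matching RFS and opposing OS.

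**Step 4, across trials.** Sets of simulated trials differing only in how many patients were converted (CR gains of 0 to 20 points) were compared, with the all-patient log OR for MRD negativity. Its correlation with the OS log HR was −0.94, the right direction. Its correlation with the RFS log HR was +0.86 to +0.93, the wrong direction. Squared, these are 0.86² = 0.74 and 0.93² = 0.86. R_T² drops the sign, so it would look strong although more MRD negativity goes with a worse RFS hazard ratio. Where trials mix conversion with real benefit in always-CR patients, the two forces oppose each other and the association can instead weaken.

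**The case against.** RFS as defined follows accepted ELN recommendations, it is secondary, no threshold is set for its R_T², and a detailed SAP is still to come. Section 2.1 asks only for association with RFS, and the individual-level analysis in 9.1.4 answers that properly. All of this stands and limits the weight of the point. It does not justify the trial-level use: a standard definition does not make the hazard ratio a randomised effect, and the current text commits to an RFS STE.

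A difference in CR rate is also an inference. Section 9.1.3 speaks of efficacy around induction and salvage, not of more remissions. A drug could deepen remissions without adding any, and RFS would then not be distorted by this route. That is why the point is conditional.

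Four stronger readings are tempting and are not supported:
- That the two axes of the RFS regression certainly describe different populations. The protocol never fixes the MRD denominator. Section 7.1 documents patients with a post-induction or post-salvage result, and Section 3.1 speaks of evaluable patients.
- That the RFS hazard ratio must reverse. With θ = 0.70 it agrees in direction with OS.
- That R_T for RFS will be low and MRD will appear to fail. Step 4 shows that R_T² can be high for the wrong reason.
- That estimating MRD in the same CR patients cures the problem. It puts the same selection on both axes and can produce spurious agreement while OS moves the other way.

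**Conclusion.** The concern holds as a flaw in a secondary analysis. As planned, the trial-level R_T² and STE for RFS rest on a comparison that randomisation does not protect whenever treatment changes the CR rate. With a 15-point CR gain and the assumed hazards, the RFS hazard ratio runs from about 1.10 to 1.15 (1.18 at most across runs) with no effect in always-CR patients, through about 0.97 to 0.99, to 0.82 to 0.85 as their true hazard ratio falls to 0.85 and 0.70. It is 1.00 if converted patients share the always-CR prognosis and treatment has no effect within that group. The direction and size depend on assumptions that the documents neither give nor exclude. What does not depend on them is that R_T² for RFS cannot be read as surrogacy: a high value may carry a wrong-signed slope, and a low one may reflect selection. The primary test on OS and the trial-level EFS analysis are not affected by this selection.

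**What to change.** In Section 9.1.4, limit the trial-level R_T² and the STE to OS and EFS, and delete RFS from the STE sentence. Keep RFS as a secondary clinical endpoint for the individual-level analysis, where MRD at CR is used to predict later RFS and conditioning on CR is appropriate. State the denominator of the MRD odds ratio in the SAP.

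If a trial-level RFS result is still wanted, label it exploratory and non-randomised, report the slope with its sign (and the coding of the odds ratio) beside R_T², and tabulate CR rates by arm for each trial. Do not present a CR-only MRD odds ratio as a remedy.

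The cost is wording in the protocol and SAP, with no new data. One secondary trial-level result is dropped or downgraded.

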9.1.3 Proposed sample size/Power calculations

For validation of MRD assessed by MPFC as surrogate endpoint for OS, it is critical that the effect of treatment on MRD assessed by MPFC is closely correlated with the effect of treatment on OS. In our previous work [43] evaluating EFS as a surrogate endpoint for OS in AML we were able to show in an individual-patient data approach of 1,811 patients from four randomized trials (AMLHD 98B [44] AMLSG 06-04, [45] AMLSG 07-04, [46] and AMLSG 12-09, [47]) with 7 independent treatment comparisons due to multiple therapeutic questions that although EFS is only moderately correlated with OS (Spearman's rho = 0.76, 95% CI: [0.73, 0.79]) the treatment effects on EFS were strongly correlated with treatment effects on OS (correlation coefficient R = 0.99, for log hazard ratios). A two-level modelling approach was used to estimate the association between EFS and OS, and between treatment effects on EFS and OS [48]. At the individual level, a bivariate (Hougaard-copula-based) survival model with Weibull marginal hazards was fitted to model the joint distribution of EFS and OS, and Spearman's rank correlation coefficient (rho) was used to quantify the association between the endpoints. At the trial-level, an error-in-variables linear regression model was fitted to the estimated treatment effects (Weibull-model-based log hazard ratios) on EFS and OS, taking into account the estimation error. The correlation coefficient (R) was used to quantify the strength of association between the treatment effects.

Study	Comparison	Control arm	Experimental arm	N
AMLSG 06-04	1	Valproic acid	Valproic acid	96
		All-trans-retinoic acid + Valproic acid		93
AMLSG 12-09	2	Standard Azacitidine prior/concurrent/after		36
	3	Standard Azacitidine after		103
AMLSG HD98B	4	Standard All-trans-retinoic acid		64
		All-trans-retinoic acid		128
AMLSG 07-04	5	Standard All-trans-retinoic acid		92
	6	Standard All-trans-retinoic acid		369
	7	Valproic acid All-trans-retinoic acid + Valproic acid		95
				91

The figure illustrates the correlation of the treatment effects on EFS and OS from 7 independent treatment comparisons as outlined and numbered in the table on the left. In this example clearly a substantial treatment effect could be demonstrated in 4 of the 7 treatment comparisons. Based on this experience we also expect treatment effects in most of the trials being part of the application. The sample size of the proposed study is fixed by the limited number of randomized trials and the trial-individual sample size calculation. We assume that 1000 patients are eligible for MRD assessment by MPFC after induction/salvage therapy. Based on i) our previous experience showing a high correlation of treatment effects on EFS and OS ($R=0.99$ for log hazard ratios with lower 95% confidence limit of 0.85), ii) the compelling data available on the prognostic value of MRD assessed by MPFC [5][21][22][23][24][25][26][27] and iii) the growing body of evidence indicating efficacy of new drugs especially in combination with induction/salvage therapy and not or to a much lesser extend later on in the treatment course (consolidation, maintenance) [10][32][49][50] the primary hypothesis is that MRD assessment by MPFC after induction/salvage therapy is a good surrogate for OS defined by trial level correlation R_T of the treatment effects on MRD assessed by MPFC and OS with $R_T > 0.8$.

We aim to test the one-sided null hypothesis $H_0: R_T \leq 0.8$ against the alternative hypothesis $H_1: R_T > 0.8$ at a significance level of $\alpha = 2.5\%$. To this aim we will use an individual patient data (IPD) meta-analytic approach and focus on the coefficient of determination (R_T)² to quantify the strength of association between treatment effects on MRD assessed by MPFC (log odds ratios, derived by logistic regression models) and treatment effects on OS (log hazard ratios, using Cox regression models) at the trial level. Based on the given sample size of at least 1000 patients within the included randomized clinical trials and considering a true R_T of 0.9 the power to identify this effect will be larger than 85%.

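### Power above 85% for the trial-level test of R_T is justified by 1000 patients, but it depends on the number of randomised comparisons, which is not stated and would have to run to dozens

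*Combined protocol and SAP*

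**What the plan says.** Section 9.1.3 sets the primary hypothesis as a one-sided test of H0: R_T ≤ 0.8 against R_T > 0.8 at 2.5%. R_T is the trial-level correlation between treatment effects on MRD and on OS. The power statement starts from patient numbers, "Based on the given sample size of at least 1000 patients within the included randomized clinical trials", and continues: "considering a true R_T of 0.9 the power to identify this effect will be larger than 85" (percent).

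The method is described as follows: "To this aim we will use an individual patient data (IPD) meta-analytic approach and focus on the coefficient of determination". Section 9.1.4 confirms that the inputs are one pair of effects per trial. Logistic models give odds ratios for MRD, and Cox models are used "for the survival endpoints resulting in per trial hazard ratios (HR"). The pairs then enter an error-in-variables "regression model of the log transformed HRs on the log transformed ORs".

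On the number of trials, section 9.1.3 says only: "The sample size of the proposed study is fixed by the limited number of randomized trials and the trial-individual sample size calculation". Section 3.1.1 names two open trials and allows others to join without an amendment. No expected or minimum number of comparisons is given. Nor is there a between-trial spread of effects, a test statistic for R_T, or a power formula or simulation. A detailed SAP is to be finalised before database closure.

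**The concern.** For a trial-level correlation the unit of information is the randomised comparison. Patients within a comparison only govern how precisely each pair of effects is estimated. A patient total therefore cannot fix the power of this test, yet it is the only sample-size input given.

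This is the only power statement for the only formally tested hypothesis. If K is small, H0 will usually stand even when R_T really is 0.9. A reader who trusts the stated power could take that non-rejection as evidence against MRD as a surrogate, when it would say very little.

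**Working it through.** **Inputs from section 9.1.3:** null boundary 0.8, true R_T 0.9, one-sided alpha 0.025, stated power above 0.85, at least 1000 patients. K is not given, so it is varied.

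**Trying to reproduce the stated figure.** Nothing in the text allows it. Two routes do exceed 85%, and neither is what the protocol describes; whether either was used is conjecture. Taking the 1000 patients as the units gives about 100%. Taking the earlier work's R = 0.99 and 7 comparisons gives Φ((2.647 − 1.099)·√4 − 1.96) = Φ(1.14) ≈ 87%, but the protocol assumes a true R_T of 0.9.

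**Idealised models, effects known without error**

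1. Fisher z: power = Φ((atanh 0.9 − atanh 0.8)·√(K − 3) − 1.96), with atanh 0.9 − atanh 0.8 = 0.3736. For 85%: K = ((1.960 + 1.036)/0.3736)² + 3 = 67.3, so 68.
2. Exact distribution of the sample correlation under bivariate-normal trial effects, with a calibrated cut-off (simulated).
3. Log odds ratios as fixed regressors: noncentral t on K − 2 degrees of freedom, with noncentrality √K·R/√(1 − R²).
4. Upper bound for any valid 2.5% test under bivariate normality: Neyman–Pearson test of 0.8 against 0.9 with means and variances known (simulated).

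| K | Fisher z | Exact correlation | Fixed regressors | Upper bound |
|---|---|---|---|---|
| 4 | 0.056 | 0.053 | 0.055 | 0.087 |
| 7 | 0.113 | 0.107 | 0.116 | 0.155 |
| 10 | 0.166 | 0.163 | 0.186 | 0.233 |
| 20 | 0.337 | 0.341 | 0.436 | 0.496 |
| 30 | 0.493 | 0.498 | 0.649 | 0.704 |
| K first reaching 85% | 68 (0.854) | 67 (0.852) | 45 (0.851) | 41 (0.853) |

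Cruder Wald and delta-method versions put the required K between 34 and 83. Those below 41 set the critical value with the variance at R = 0.9 rather than at the null, so they do not hold the 2.5% level. Every version needs dozens of comparisons.

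**Splitting the 1000 patients.** 1000/45 = 22.2 and 1000/68 = 14.7 patients per comparison. Assume 1:1 allocation, 50% MRD-positive and 60% deaths. Then SE(log OR) = 4/√n, about 0.85 to 1.04, and SE(log HR) = 2/√(0.6n), about 0.55 to 0.67.

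The upper bound was recomputed with this estimation error and equal comparisons. The assumed SD of true log ORs was 0.5–1.5, that of true log HRs 0.3–0.75, and the error correlation 0–0.5. The bound is then 0.035 to 0.22 at every K tried from 4 to 67. With 2000 patients it is 0.046 to 0.43.

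**Scale of the earlier EFS/OS work.** It was an "individual-patient data approach of 1,811 patients from four randomized trials" with 7 comparisons. If all patients entered those comparisons, that is 1811/7 = 258.7 each. At that size 1000 patients supply 1000/258.7 = 3.9 comparisons.

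**Precision of the earlier work.** It reports R = 0.99 "for log hazard ratios with lower 95% confidence limit of 0.85". Read as a two-sided limit on the z scale, the SE is (atanh 0.99 − atanh 0.85)/1.96 = 0.709. If that precision carried over to MRD and OS, power would be Φ(0.3736/0.709 − 1.96) = 0.076, or 0.062 to 0.090 allowing for rounding of 0.99.

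**The case against.** **No arithmetic slip is shown.** With no K and no formula, there is no calculation to find wrong, and an unreported simulation may exist. This is fair: the finding is that the figure is unsupported by its stated basis and implausible for a limited number of trials. But under bivariate-normal trial effects such a simulation would have needed at least about 41 comparisons, even before estimation error.

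**K of 4 to 10 is the reviewer's choice.** True. The protocol sets no maximum, and the 7 comparisons belong to other work. The required K of 45 to 68, and the bound of 41, do not depend on that range.

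**The earlier work is a weak guide.** This largely stands. EFS and OS share death as an event, unlike a binary MRD result and OS. A plain Fisher interval for R = 0.99 with 7 units has a lower limit of 0.93, not 0.85, so the reported limit does not follow the simple z model. The table of comparison sizes is also damaged in the available text. The 8% and the 259 per comparison are illustrations only, and the conclusion does not need them.

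**The practical weight is limited.** The power figure does not drive recruitment, the study is non-interventional, individual-level measures and the surrogate threshold effect are also planned, and the SAP is still to come. Nothing in the text says that non-rejection will be read as evidence against surrogacy. These points soften the consequence, but they do not support a specific power figure already attached to the primary hypothesis.

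**Conclusion.** The concern holds. Power above 85% at a true R_T of 0.9 does not follow from 1000 patients and cannot be reproduced. Idealised models need about 45 to 68 comparisons, and about 41 is the floor for any valid test with bivariate-normal trial effects. The protocol describes its trials as limited in number and names two as open.

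For an assumed K of 4 to 10, power is about 5–19% under the correlation and fixed-regressor models, so H0 would stand in about 81–95% of such studies at the protocol's own planning value. Any valid test is capped at 23%. With estimation error from 1000 patients, under the assumed rates and spreads, the cap is 4–22% across the K tried.

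The required-K figures rest on the protocol's own alpha, null and alternative, and on the idealised models named. They are not the power of the planned error-in-variables analysis, for which no test statistic is given.

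**What to change.** Remove the claim of power above 85% from section 9.1.3. Keep the hypothesis, alpha and patient numbers. Replace the claim with text such as:

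> Power depends on the number of randomised comparisons K. We expect K = [state], with about [state] patients each. The test statistic for R_T is [state]. At a true R_T of 0.9, the power of the planned error-in-variables analysis is [x]% by simulation, assuming [comparison sizes, MRD-positive rate, death rate, between-trial spread of log ORs and log HRs]. R_T and its square will be reported with 95% confidence intervals alongside the surrogate threshold effect. With few comparisons, non-rejection of H0 is inconclusive and is not evidence against surrogacy.

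If a power table by K is added from the idealised correlation test, label it as a benchmark with bivariate-normal trial effects and no estimation error, not as the power of the planned analysis.

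The cost is one rewritten passage, a stated test statistic and one simulation, which fits the SAP due before database closure. No patients are added. The price is a much less favourable stated power.
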